7.1 Study flow and visit schedule

Table 7-1 list all the assessments and indicates with an “X”, the visits when they are performed. All data obtained from these assessments must be supported in the patient’s source documentation.

Screening evaluation must be performed ≤ 28 days of cycle 1 Day 1 except for the pregnancy test which is to be performed within 3 days prior to the first dose of study treatment. Laboratory and radiological assessments performed as part of standard of care prior to signing informed consent

may be used if performed within the screening time window. The time window for tumor biopsies in the Phase I/II may be longer than 28 days.

During the course of the study visits, test and/or procedures should occur on schedule whenever possible. From C2D8, a visit window of +/- 3 days is allowed (with the exception of 30 days safety follow-up visit, for which a visit window of +7 days is allowed).

There is a +/- 7 days window on, tumor response assessment and chest radiological examination after starting study drug.

In particular, full PK sampling with multiple post-dose time points on Day 1 and Day 15 of cycle 1 and other days should be performed on the specified days. (Please refer to PK sampling schedule [Table 7-7-2](#) and [错误!未找到引用源。7-3](#)). The first three patients should perform single dose full PK sample collecting in the first day.

The assessment type please see [Section 7.2](#).

Unscheduled visit: Additional visits can be performed as appropriate and at the discretion of the investigator

Table 7-1 Visit evaluation Schedule of Assessments and Procedures

Visit name	Protocol Section	Screening period		Study treatment period								follow up period			
		0 molecu lar screeni ng		Cycle 1 Day 1 through 21			Cycle 2 Day 22 through 42			Cycle 3-X 21d/cycle, visit on 1st day of every 2 cycles	End of treatment visit (EOT)/early discontinuation (Section 7.1.4)	Safety follow up	Progress Disease follow up	Survival follow-up (Section 7.1.5.2)	
Visit Day		1 Screening		-28 to -1	1 ± 0	8 ± 1	15 ± 1	22 ± 1	29 ± 3	36 ± 3	43 ± 3	N/A	+ 7	±7	±7
Obtain molecular screening consent (Phase I expansion and Phase II extension)	7.1.1	X													
Informed consent	7.1.2		X												
Inclusion/exclusion criteria	5.2, 5.3		X												
Biomarker detection	7.1.1	X ¹	X												
Medical history/tumor history/tumor treatment history	7.1.2.2		X ²	X	X	X	X	X	X	X	X				
Tumor diagnosis and severity	7.1.2.2		X												

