7.2.2 Pharmacokinetics

7.2.2.1 Blood sample schedule

Study drug will be taken QD at cycle1 day 1 and twice daily from the second day of cycle 1 in the first 3 patients. First dose in clinic on days when PK sampling occurs i.e., Cycle 1 Day 1 and Cycle 1 Day15, remaining doses on all other days to be self-administered by patient.

In order to detect PK of a single administration, for the first 3 patients, a single administration will be given on the first day, administration twice daily from the second day. Patients will undergo serial blood sampling 2ml for PK analysis during cycle 1 on day 1 at pre-dose and 15min, 30min, 1, 2, 3, 4, 6, 8 hours post-dose, and 12 hours post-dose (if available); on day 2 at pre-dose; on cycle1 day 7 (pre-dose), cycle1 day 10 (pre-dose), day 15 at pre-dose and 15min, 30min, 1, 2, 3, 4, 6, and 8 hours post-dose, and 12 hours post dose (if available); and day 16 at pre-dose. On day 22, prior to dose administration, a final blood sample was collected for pharmacokinetic analyses. See [Table 7-2](#), [错误!未找到引用源。3](#).

Serial blood samples will be collected from all patients to assess single dose and multiple dose plasma PK of HH2710 and its metabolite. PK parameters will be derived from each individual plasma concentration-time profiles. Refer to [Section 10.6.4](#) for list of PK parameters that will be estimated.

PK blood sample collection and handling

Blood samples will be taken by either direct venipuncture or an indwelling cannula inserted in a forearm vein. At specified time points described in [Table 7-2](#) and [错误!未找到引用源。3](#), 2 mL blood draws will be collected into tubes containing K2 EDTA and gently inverted several times to thoroughly mix the anticoagulant. Tubes will be centrifuged to separate plasma and plasma will

immediately be transferred into labeled 2 mL polypropylene screw-cap tubes. Plasma samples will be placed in a freezer in an upright position until shipment to the bioanalytical laboratory for analysis.

All sampling is relative to the ingestion of HH2710. On days and time points where blood PD samples are to be drawn, the PK sample must be drawn first. The exact collection date and time of all samples must be documented on the PK blood collection CRF pages. The date and exact time of dosing, as well as the date and actual time of blood sampling must be recorded on the CRF.

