Refer to the [HH2710-G101 Laboratory Manual] for detailed instructions for the collection, handling, and shipment of PK samples.

Intensive PK sampling will be done in the dose escalation portion of the trial. Additional PK sampling will be drawn every two cycles prior to Day 1 dosing in all patients in the dose escalation between Cycle 1 to Cycle 9 (e.g. Cycle 3 Day 1, Cycle 5 Day 1, Cycle 7 Day 1, Cycle 9 Day 1) ([Table 7-2](#)).

PK samples at pre-dose, 2h, 4h, a 6h, 8h, and 24h post dose will also be obtained at Cycle 1 Day 1 and Cycle 1 Day 15 for patients in the Phase I dose expansion stage and Phase II portions of the trial ([Table 7-3](#)).

Table 7-2: PK blood sampling time for Phase I dose escalation stage

CxDx	C1D1	C1D1	C1D1	C1D1	C1D1	C1D1	C1D1	C1D1	C1D1	C1D2	C1D7	C1D10	C1D15	C1D15	
No.	1	2	3	4	5	6	7	8	9	10	11	12	13	14	15
Time	pre-dose	15min	30min	1h	2h	3h	4h	6h	8h	12h (If available)	24h (pre-dose)	pre-dose	pre-dose	pre-dose	15min
Window (min)	-30	±5	±5	±5	±10	±10	±10	±30	±30	±60	-30	-30	-30	-30	±5
Blood Sampling	2mL	2mL	2mL	2mL	2mL	2mL	2mL	2mL	2mL	2mL	2mL	2mL	2mL	2mL	2mL
CxDx	C1D15	C1D15	C1D15	C1D15	C1D15	C1D15	C1D15	C1D15	C1D16	C2D1	C3D1	C5D1	C7D1	C9D1	NA
No.	16	17	18	19	20	21	22	23	24	25	26	27	28	29	NA
Time	30min	1h	2h	3h	4h	6h	8h	12h (If available)	pre-dose	pre-dose	pre-dose	pre-dose	pre-dose	pre-dose	NA
Window(min)	±5	±5	±10	±10	±10	±30	±30	±60	-30	-30	-30	-30	-30	-30	NA

Blood Sampling	2mL	NA											
----------------	-----	-----	-----	-----	-----	-----	-----	-----	-----	-----	-----	-----	----

Table 7-3: PK blood sampling time for Phase I dose expansion stage and Phase II

CxDx	C1D1	C1D1	C1D1	C1D1	C1D1	C1D2	C1D15	C1D15	C1D15	C1D15	C1D15	C1D15
No.	1	2	3	4	5	6	7	8	9	10	11	12
Time	pre-dose	2h	4h	6h	8h	24h	pre-dose	2h	4h	6h	8h	24h
Window(min)	-30	±10	±10	±30	±30	±60	-30	±10	±10	±30	±30	±60
Blood Sampling	2mL	2mL	2mL	2mL	2mL	2mL	2mL	2mL	2mL	2mL	2mL	2mL

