10.6.4 Pharmacokinetic Analysis

Samples for PK analysis of HH2710 and its metabolite will be obtained from all patients enrolled in Phase I dose escalation/expansion and Phase II trial.

Below is the list of PK parameters that will be calculated after single dose (C1D1) and steady State (C1D15).

Table 10-2 PK Parameters Description

PK Parameter (plasma)	Description
C _{max}	Peak plasma concentration determined manually by visual inspection of plasma concentration vs. time figures on the untransformed (linear) scale of measurement
t _{max}	Time to reach the peak plasma concentration determined manually by visual inspection of plasma concentration vs. time figures on the untransformed (linear) scale of measurement
AUC ₀₋₂₄	Area under the plasma concentration-time curve from 0 to 24 hours post-dose, calculated by linear/log trapezoidal method
AUC _{0-∞}	Area under the plasma concentration-time curve from time zero to infinity after dosing calculated by linear/log trapezoidal method
%AUC _{extrap}	Area under the plasma concentration-time curve extrapolated from time t to infinity as a percentage of total AUC (%)
Lambda _z (λ _z)	Terminal phase rate constant, determined by linear regression of at least 3 points on the terminal phase of the log-linear plasma concentration-time curve. The correlation coefficient (r ²) for the goodness of the fit of the regression line through the data points has to be 0.85 or higher for the value to be considered reliable. If the WinNonlin data points are not on the linear portion of the terminal slope, the data points will be selected manually prior to calculation of Lambda _z
t _{1/2}	Terminal half-life, defined as 0.693 (ln2) divided by Lambda z
CL/F	The apparent total body clearance of drug from the plasma (volume x time-1)
V _z /F	The apparent volume of distribution during terminal phase (associated with λ _z)(volume)

Descriptive statistics [n, arithmetic mean, standard deviation, coefficient of variation (CV), median, minimum, maximum, geometric mean, geometric standard deviation geometric CV] will be used

to summarize PK parameters by treatment. For $t_{1/2}$ and t_{max} , regular descriptive statistics and 95% confidence intervals about the arithmetic mean will be calculated, if possible, for each dose. Refer to the PK analysis plan for additional details regarding with the PK analyses.

A listing of blood PK concentrations and parameters will be provided.

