8.9 Pharmacokinetic Analysis

Pharmacokinetic parameters will be determined with non-compartmental analysis method with PK Analysis Set.

Samples for PK analysis of HH2710 and selected metabolites will be obtained from all Phase I/II patients during their first cycle of treatment (Cycle 1). PK samples will also be obtained from additional patients in Phase II depending on the outcome of initial PK analysis.

Below is the list of various PK parameters that will be calculated after Dose 1 (Day 1) and at Steady State (Day 22).

Table 2 PK parameters Description

PK Parameter (plasma)	Description
C_{\max}	Peak plasma concentration determined manually by visual inspection of plasma concentration vs. time figures on the untransformed (linear) scale of measurement

t_{max}	Time to reach the peak plasma concentration determined manually by visual inspection of plasma concentration vs. time figures on the untransformed (linear) scale of measurement
AUC_{0-12}	Area under the plasma concentration-time curve from 0 to 12 hours postdose, calculated by linear/log trapezoidal method
AUC_{0-last}	Area under the plasma concentration-time curve from time 0 to time of last observation after dosing calculated by linear/log trapezoidal method
Lambda_z (λ_z)	Terminal phase rate constant, determined by linear regression of at least 3 points on the terminal phase of the log-linear plasma concentration-time curve. The correlation coefficient (r^2) for the goodness of the fit of the regression line through the data points has to be 0.85 or higher for the value to be considered reliable. If the WinNonlin data points are not on the linear portion of the terminal slope, the data points will be selected manually prior to calculation of Lambda_z
$t_{1/2}$	Terminal half-life, defined as $0.693 / \lambda_z$
CL/F	The total body clearance of drug from the plasma (volume x time-1)
V_z/F	The apparent volume of distribution during terminal phase (associated with λ_z)(volume)

Descriptive statistics [n, arithmetic mean, standard deviation, coefficient of variation (CV), median, minimum, maximum, geometric mean, geometric standard deviation geometric CV] will be used to summarize PK parameters by treatment. For $t_{1/2}$ and t_{max} , regular descriptive statistics and 95% confidence intervals about the arithmetic mean will be calculated, for each dose.

A listing of blood PK concentrations and parameters will be provided.

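### SAP 8.9 sets steady-state PK on Day 22, when no post-dose sample is taken; the protocol's profile day is Cycle 1 Day 15

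*SAP*

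**What the plan says.** SAP 8.9 introduces its parameter table by stating that the values will be "calculated after Dose 1 (Day 1) and at Steady State (Day 22". The table lists eight parameters: Cmax, tmax, AUC0-12, AUC0-last, lambda_z, t1/2, CL/F and Vz/F.

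Protocol 10.6.4 names a different second day. It refers to the "PK parameters that will be calculated after single dose (C1D1) and steady State (C1D15".

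The sampling schedule agrees with Protocol 10.6.4:

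- Protocol 7.1 describes "full PK sampling with multiple post-dose time points on Day 1 and Day 15 of cycle 1".
- Protocol 7.2.2.1, on serial sampling, lists "day 15 at pre-dose and 15min, 30min, 1, 2, 3, 4, 6, and 8 hours post-dose", with a 12-hour sample if available and a pre-dose sample on Day 16.
- The same section says of Day 22: "On day 22, prior to dose administration, a final blood sample was collected for pharmacokinetic analyses". Table 7-2 agrees, with a single Cycle 2 Day 1 pre-dose entry (sample 25).
- For the later parts, Protocol 7.2.2.1 says samples "will also be obtained at Cycle 1 Day 1 and Cycle 1 Day 15 for patients in the Phase I dose expansion stage"; the same sentence covers Phase II. Table 7-3 has no Day 22 sample.

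The schedule of assessments in Protocol 7.1 identifies Day 22 as the start of the second cycle ("Cycle 2 Day 22 through 42").

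**The concern.** The SAP attaches a full set of non-compartmental parameters to a day without a concentration-time profile. Cmax, tmax and AUC need post-dose concentrations. By the SAP's own definition, lambda_z needs at least three terminal-phase points; t1/2 and Vz/F depend on lambda_z, and CL/F depends on AUC. One trough supplies none of these.

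PK is the only secondary objective of Phase I, and the endpoint sections of both documents list PK among the inputs to the recommended Phase II dose. If the SAP were applied as worded, the steady-state half of the PK output would be empty. If the analyst silently used Day 15 instead, the report would depart from the SAP with no documented change.

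**Working it through.** There is no planned figure to reproduce, so the check is a count of scheduled samples against what each parameter needs.

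**1. Which visit is Day 22?** Cycles last 21 days, so Cycle 2 Day 1 is study day 21 + 1 = 22. SAP 8.9 also says that samples come from the first cycle, and Day 22 lies outside it. The SAP section therefore disagrees with itself as well as with the protocol.

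**2. Samples by day** (Protocol Tables 7-2 and 7-3, with 7.2.2.1):

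| Day | Escalation | Expansion and Phase II |
|---|---|---|
| C1D1 | 10 | 5 |
| C1D2 | 1 | 1 |
| C1D7, C1D10 | 1 each | 0 |
| C1D15 | 10 (12 h only if available) | 6 (the 24 h sample falls on the next day) |
| C1D16 | 1 | counted under C1D15 |
| C2D1 (Day 22) | 1, pre-dose | 0 |
| C3D1, C5D1, C7D1, C9D1 | 1 each, pre-dose | 0 |
| Total | 29 | 12 |

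The totals agree with the table numbering: 10 + 1 + 2 + 10 + 1 + 1 + 4 = 29, and 5 + 1 + 6 = 12.

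**3. Post-dose samples against need:**

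- Day 22, escalation: 1 − 1 pre-dose = 0 post-dose.
- Day 22, expansion and Phase II: 0.
- Day 15, escalation: 10 − 1 = 9 post-dose, plus the Day 16 pre-dose sample.
- Day 15, expansion and Phase II: 6 − 1 = 5 post-dose.

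On Day 22 none of the eight parameters in the SAP table can be derived. That is seven kinds of parameter if AUC is counted once, as in the Phase I endpoint list. On Day 15 every part has more than three post-dose points scheduled, so a profile is available. Whether a particular lambda_z fit meets the SAP's r² threshold of 0.85 depends on the data.

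**4. Is Day 15 late enough to be steady state?** Protocol 2.3 reports a half-life of 8.42 to 10.9 h. Five half-lives are 5 × 8.42 = 42.1 h to 5 × 10.9 = 54.5 h, or 1.8 to 2.3 days. The Day 15 pre-dose sample comes 14 × 24 = 336 h after the first dose.

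Protocol 2.3 also reports 3- to 4-fold accumulation, which points to a longer effective half-life. As a stress test, assume a one-compartment model, once-daily dosing and 4-fold accumulation. Then 1/(1 − e^(−24k)) = 4 gives e^(−24k) = 0.75, so the half-life is 24 × ln 2 / ln(1/0.75) = 57.8 h. Five of these are 289 h (12.0 days), still short of 336 h. Steady state therefore gives no reason to move the profile day to Day 22.

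**5. Was the move declared?** SAP 8.12 lists departures from the protocol as minor as the number of decimals for percentages. It does not mention a change of PK day.

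**The case against.** The strongest reply is that this is a mislabelled day with little practical effect. The Day 15 profiles are scheduled in every part, and a PK analyst who found no Day 22 profile would turn to Day 15. The protocol already reports steady-state accumulation at the January 2022 cut-off, so steady-state exposure was evidently being derived. Protocol 10.6.4 also refers to a separate PK analysis plan that may name the right day, and SAP section 7 warns that early termination may leave many analyses undone. Finally, the objective is worded as characterising the PK profile without mention of steady state, and the Day 1 profile can serve that wording.

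Much of this stands as a limit on the consequence. No data are lost, the Day 1 results are unaffected, and the objective remains attainable. It does not cure the text. SAP 8.9 states its own day and does not defer to another plan. Early termination does not explain a wrong day, and PK data from 22 patients were already in hand. Relying on the analyst to override the SAP is the undocumented departure that a SAP is meant to prevent.

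One passage might seem to support Day 22: Protocol 7.2.1.7 schedules post-dose ECGs on Cycle 2 Day 1 and says ECG times match PK times. Since no post-dose PK sample is listed for that day, this is a further mismatch to reconcile and not evidence of a profile.

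**Conclusion.** The concern holds. As written, the SAP's steady-state calculation cannot produce any of its tabulated parameters, in any patient, on the day it names. Day 22 has one trough in escalation and nothing in expansion or Phase II. The failure follows from applying the SAP literally, so it is not a forecast of lost data. The conclusion rests on the sampling tables being the operative schedule, and the text of Protocol 7.1 and 7.2.2.1 supports them. It is a correctable inconsistency between SAP and protocol that should be resolved before the PK analysis is run.

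**What to change.** In SAP 8.9, change the steady-state day from Day 22 to Cycle 1 Day 15, matching Protocol 10.6.4. State that the pre-dose samples on C2D1, C3D1, C5D1, C7D1 and C9D1 are summarised only as trough concentrations. For the day itself this is one line of wording, with no new data and no protocol amendment.

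Two neighbouring points can be settled in the same edit, though they are separate matters:

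- **AUC intervals.** The SAP table uses AUC0-12 and AUC0-last, whereas Protocol Table 10-2 uses AUC0-24 and AUC0-∞, and SAP 8.12 does not list the difference. The 12-hour sample is only taken if available in escalation and is absent in expansion and Phase II. The intervals should be reconciled with the sampling actually scheduled.
- **ECG timing.** The statement in Protocol 7.2.1.7 that ECG times match PK times should be reconciled with the absence of post-dose PK samples on Cycle 2 Day 1.

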8.10 Pharmacodynamics Analysis

Pending for medical confirmation.

8.11 Exploratory Biomarker Endpoints Analysis

If there exists exploratory biomarker endpoints analysis, it will be included in separate analysis documents.

8.12 Changes From Protocol-specified Analyses

1 year survival rate instead of 1 year overall survival time will be summarized in SAP.

Percentages will be presented to 1 decimal place unless otherwise specified in SAP.

For baseline characteristics, SAP will present Previous Anti-tumor Therapy Type: medication, surgery and radiotherapy instead of previous chemotherapy and previous immunotherapy.

Updated Safety Set to Safety Analysis Set and All-Treated Set to Full analysis set and keep the algorithm the same as protocol.

Members of the review committee will be internal and external to the sponsor.

Remove “Final Analysis section”. By default, primary analyses are final analysis.

Remove “Percentages will be rounded to the nearest whole number (zeroes are not displayed) with values of “< 1%” and “> 99%” shown as necessary for values falling near the boundaries” from general principles section.

9. Literature Citations / References

Clopper CJ and Pearson ES. The use of confidence or fiducial limits illustrated in the case of the binomial. *Biometrika.* 1934; 26(4):404-413.

Liu S, et al., Bayesian Optimal Interval Designs for Phase I/II Clinical Trials. *Journal of the Royal Statistical Society.* 2015, 64(3): 507-523

10. Appendices

10.1 Appendix A Censor rule for PFS, DoR

No.	Situation	Events or Censor	Analysis date*
1	No baseline assessment	Censor	First dose date
2	No post-baseline assessment, no Death	Censor	First dose date
3	PD during the study (except #5, #7)	Events (PD)	PD date
4	Any kind of Death (except #5, #7)	Events (Death)	Death date
5	PD or Death after missed two consecutive assessment	Censor	Last assessment date before the missed two consecutive assessment
6	Have at least one post-baseline assessment, no PD, no Death	Censor	Last assessment date
7	Initiating alternative anti-cancer therapy	Censor	Last assessment date before initiating alternative anti-cancer therapy

* If there are multiple assessment date on one tumor assessment, choose the earliest assessment date when overall response is PD, and choose the latest assessment date when overall response is CR/PR/SD.

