7.1.5.2 Follow-up of survival

Telephone follow-up will be conducted every 3 months since the occurrence of progressive disease or the starting of new antitumor treatment to collect patients' information on subsequent antitumor treatment and survival condition. It was completed 1 year after disease progression or initiation of new anti-tumor therapy. If patients have started new antitumor treatment after the final dose prior to end-of-treatment visit, they will directly enter the survival visit without receiving the end-of-treatment visit.

If patients terminate treatment prior to the occurrence of progressive disease, they should take part in survival follow-up to collect patients' information on subsequent antitumor treatment and survival condition.

Patients lost to follow up should be recorded as such on the CRF. For patients who are lost to follow-up, the investigator should show "due diligence" by documenting in the source documents steps taken to contact the patient, e.g., dates of telephone calls, registered letters, etc.

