10.2 Appendix B Censor rule for TTR

No.	Situation	Events or Censor	Analysis date*
1	CR, PR before PD, Death, alternative anti-cancer therapy or missed two consecutive assessment.	Events	First CR, PR date
2	No CR/PR/ alternative anti-cancer therapy/ missed two consecutive assessment/PD/Death	Censor	Last assessment date
3	No CR/PR, have PD or Death	Censor	First date of PD or Death
4	No CR/PR before alternative anti-cancer therapy	Censor	Last assessment date before initiating alternative anti-cancer therapy
5	No CR/PR before missed two consecutive assessment	Censor	Last assessment date before the missed two consecutive assessment

* If there are multiple assessment date on one tumor assessment, choose the earliest assessment date when overall response is PD, and choose the latest assessment date when overall response is CR/PR/SD.

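### SAP Appendices A and C give row 7 no time order, so read literally a documented progression followed by another anti-cancer therapy is censored instead of counted as a PFS, DoR or TTP event

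*SAP*

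**What the plan says.** SAP Appendix A sets the rules for PFS and DoR.

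- Row 3 makes progression an event, subject to an exception: "PD during the study (except #5, #7".
- Row 4 does the same for death: "Any kind of Death (except #5, #7".
- Row 7 is a censoring row. Its situation is only "Initiating alternative anti-cancer therapy", and its analysis date is "Last assessment date before initiating alternative anti-cancer therapy".

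Appendix C repeats rows 3 and 7 for TTP; there, death in row 4 is a censoring reason.

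Neighbouring rows do state an order or a condition. Row 5 of the same table reads "PD or Death after missed two consecutive assessment". Row 6 requires that neither progression nor death has occurred. In Appendix B (TTR), row 1 reads "CR, PR before PD, Death, alternative anti-cancer therapy or missed two consecutive assessment" and row 4 reads "No CR/PR before alternative anti-cancer therapy".

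Appendix E defines PFS as running from first dose to objective progression or death, whether or not another anticancer therapy was received before progression. It defines TTP as running to the first documented progression, and it ties the end of DoR to the date used for PFS. Protocol 10.6.8 censors DoR only in patients without documented progression. SAP 8.12, which lists changes from the protocol, does not mention a change to that rule.

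**The concern.** Rows 3 and 4 exclude everyone who meets row 7, and row 7 is met by starting another therapy at any time. A patient whose progression comes first therefore loses the event because of something that happened afterwards. No definition in either document calls for that.

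The sequence is an ordinary one. Protocol 6.4.3 bars other anticancer treatment while on study, and radiographic progression is the first reason listed in 7.1.4.1 for stopping treatment. New therapy will therefore often follow progression. The data that would trigger row 7 are collected: protocol 7.1.5.2 has sites telephone every 3 months after progression or the start of new treatment for "information on subsequent antitumor treatment and survival condition", and SAP 8.5 plans a summary of post-treatment anti-tumour medication. A program that follows the table as written would find these records and switch row 3 off. PFS, TTP and DoR would all come out too long.

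**Working it through.** **1. Applying the rows.** Take progression documented at week 12 and a new therapy started at week 14.

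| Step | Literal reading | With time order |
|---|---|---|
| Row 7 met? | Yes: a new therapy was started | No: the therapy came after progression |
| Row 3 available? | No: row 7 is an exception | Yes |
| Result | Censored at the last assessment before week 14 | Event at week 12 |

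If the progression scan is the last scan before the new therapy, the literal censoring date is week 12. If another scan falls in between, for example at the end-of-treatment visit (protocol 7.2.5), the date moves later. The event is lost either way.

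Row 4 adds nothing separate here. A therapy cannot start after death, so the missing order matters only for patients who progress, start a therapy and then die. For them progression should already have been the event.

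**2. Direction.** The Kaplan-Meier factor at each time is 1 − d/r, with d events among r at risk. Recoding an event at time T as a censoring at T or later lowers d at T and never reduces r. Every factor stays the same or rises, so the curve can only move up.

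**3. Hand example (constructed data).** Ten patients progress at weeks 6, 6, 6, 12, 12, 12, 18, 18, 24 and 30. Five of them start new therapy after progression: two of those at week 6, and one each at weeks 12, 18 and 24.

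- Correct coding: S(6) = 7/10 = 0.70 and S(12) = 0.70 × 4/7 = 0.40. The median is 12 weeks.
- Literal coding: S(6) = 9/10 = 0.90, S(12) = 0.90 × 5/7 = 0.643 and S(18) = 0.643 × 3/4 = 0.482. The median is 18 weeks.

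**4. Size.** The documents state no expected median, event count or uptake of later therapy for these endpoints, so there is no plan figure to reproduce. The scan interval is from the plan: two 21-day cycles, so g = 42/30.4375 = 1.38 months. Everything else is assumed.

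*Set A.* 36 patients (the planned maximum for cohorts 1 and 2), exponential PFS with median m = 4 months, every event a progression, 18 months of follow-up. A share f of progressors, unrelated to time of progression, starts new therapy before any further scan.

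- Event probability per scan: h = 1 − 2^(−g/m) = 1 − 2^(−0.345) = 0.213.
- Under the literal rule the estimated probability is (1 − f)h. The median is the first scan k with [1 − (1 − f)h]^k ≤ 0.5.
- Thirteen scans fit into 18 months, so expected events under correct coding are 36 × (1 − 0.787^13) = 34.4. The literal count is (1 − f) times that.

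| f | Events | First k | KM median (months) |
|---|---|---|---|
| 0 | 34.4 | 3 | 4.1 |
| 30% | 24.1 | 5 | 6.9 |
| 50% | 17.2 | 7 | 9.7 |
| 70% | 10.3 | 11 | 15.2 |

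Simulation under the same assumptions gives the same medians and event counts, to within 0.1 of an event.

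*Set B.* A simulation of 20,000 patients with true median 4.1 months, 85% of events being progressions (the rest deaths), and a 12-month cut-off.

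| f | Patients with event, correct / literal | KM median, correct / literal (months) | 6-month PFS, correct / literal |
|---|---|---|---|
| 25% | 85% / 67% | 4.1 / 5.5 | 0.39 / 0.49 |
| 50% | 85% / 49% | 4.3 / 8.3 | 0.40 / 0.60 |
| 75% | 85% / 31% | 4.1 / 11.1 | 0.39 / 0.72 |

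At f = 0 the two rules agree. Medians move largely in scan steps of about 1.4 months, so small differences in uptake can look larger than they are.

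**The case against.** The best defence is that the tables are shorthand and should be read with the definitions. SAP 8.7.1.3 refers to the censoring appendices and to Appendix E together. Under Appendix E the clock stops at first progression, so the sensible meaning of the row 7 exception is progression or death after new therapy. Appendix B is loose in a similar way: a patient without response who progresses and then starts a new therapy meets both its row 3 and its row 4, with no stated precedence. Many programmers would apply the usual convention.

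That makes the intended meaning likely, but it does not put it in the text. Appendix E does not supply the missing order; its PFS definition disagrees with row 7 altogether, because it counts progression even after another therapy. The tables are the operative rule, and as written they give the wrong answer.

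Other parts of the objection stand. The medians depend wholly on assumed inputs. PFS, DoR and TTP are secondary in Phase II, PFS and DoR are exploratory in Phase I, and none carries a hypothesis. SAP section 7 says the programme has stopped and many planned analyses may not be conducted, and 8.7.1.3 makes the Kaplan-Meier work conditional on adequate numbers. The same section does still plan listings of all time-to-event endpoints, where a wrong event flag would show.

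**Conclusion.** The point holds as a wording defect with a definite direction. Taken literally, rows 3, 4 and 7 censor a documented progression because of a therapy started later, against SAP Appendix E and protocol 10.6.8, and the result always favours the drug.

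The size is not known. At 50% uptake and a true median of about 4 months, the two sets of assumptions give 8.3 and 9.7 months. These show sensitivity; they do not predict this study. DoR and TTP are affected in the same direction but were not simulated.

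A reader might infer three stronger things that the documents do not support:

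- That every affected patient is censored on the progression date. A later scan before the new therapy moves the date.
- That reported medians will be inflated to 10 or 15 months. This needs uptake figures the documents do not contain and a program that follows the literal text.
- That the efficacy decision is compromised. ORR and the BOP2 stopping boundaries do not use these tables.

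**What to change.** In Appendices A and C:

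- Change row 7 to *New anti-cancer therapy started before documented PD or death*.
- Limit the exceptions in rows 3 and 4 to progression or death occurring after the start of new therapy, or after two consecutive missed assessments.
- State that a therapy started on or after the progression date leaves the progression as an event, so that a same-day start is not left without a row.
- Keep death as a censoring reason for TTP.

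In the same edit, reconcile row 7 with the Appendix E definition of PFS. Either censoring at new therapy is the main rule and Appendix E is amended, or Appendix E stands and row 7 becomes a sensitivity analysis. The time order alone does not settle this. If row 7 is kept for DoR, list it in SAP 8.12 as a change from protocol 10.6.8.

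The cost is a small wording change in the SAP, plus a check of the derivation code in case row 7 has already been programmed literally. No new data are needed.
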